Old text:

Section 7.6.2 Biomarker investigation (pharmacogenetics) (~~optional~~ – consent required) (as of Amd 4)

The purpose of this genetic analysis is to identify markers for risk of inhibitor development in subjects treated with BAY 81-8973. The markers to be analyzed are type of FVIII gene mutation if not available, single nucleotide polymorphisms (SNPs) in immunoregulators (eg, IL 10), HLA genotype, and FVIII polymorphisms. This biomarker analysis is exploratory and will be analyzed for PUPs and MTPs only. (as of Amds 4 and 6)

A separate informed consent for pharmacogenetic sampling is required and participation is ~~optional~~. (as of Amd 4)

If a subject elects to participate, a blood sample can be collected at any visit except Screening, ideally at Visit 3 or whenever the subject's body weight/condition is suitable for an additional blood draw. Samples will be prepared and labeled according to laboratory specifications. Details of the sample collection and shipment procedures will be provided in the Laboratory Manual. (as of Amd 4)

A subject does not need to agree to participate in the pharmacogenetic sub-study to be enrolled in the main study. (as of Amd 4).

New text:

Section 7.6.2 Biomarker investigation (pharmacogenetics) (recommended – consent required) (as of Amd 4 and Amd 7)

The purpose of this genetic analysis is to identify markers for risk of inhibitor development in subjects treated with BAY 81-8973. The markers to be analyzed are type of FVIII gene mutation if not available, single nucleotide polymorphisms (SNPs) in immunoregulators (eg, IL 10), HLA genotype, and FVIII polymorphisms. This biomarker analysis is exploratory and will be analyzed for PUPs and MTPs only. (as of Amds 4 and 6)

A separate informed consent for pharmacogenetic sampling is required and participation is recommended. (as of Amd 4 and Amd 7)

If a subject elects to participate, a blood sample can be collected at any visit except Screening, ideally at Visit 3 or whenever the subject's body weight/condition is suitable for an additional blood draw. Samples will be prepared and labeled according to laboratory specifications. Details of the sample collection and shipment procedures will be provided in the Laboratory Manual. (as of Amd 4)

A subject does not need to agree to participate in the pharmacogenetic sub-study to be enrolled in the main study. (as of Amd 4). However, as this analysis provides important information about inhibitor development, participation in the sub study is recommended. (as of Amd 7)

13.6 Amendment 8

Amendment 8 is the sixth global amendment dated 01 FEB 2019, and is presented using a different approach from the previous amendments. The rationale for this amendment with an overview of the affected sections is provided in the “[Protocol Amendment Summary of Changes Table](#)” which can be found directly before the Table of contents in this document.

[figure not shown]
Changes in this document are made without annotations. A separate file with tracked changes against the last integrated protocol version is available upon request.

14. Appendices

14.1 Instruction for use of study medication

14.1.1 Presentation of vials with Bio-SET reconstitution cap

- Study medication is intended for intravenous administration only and must be administered immediately after reconstitution.
- You must use aseptic conditions (meaning clean and germ free) during reconstitution and administration. Use only the medical devices (powder vial with Bio-Set device, pre-filled syringe containing solvent and venipuncture set) for reconstitution and administration that are provided with each package of study medication.
- Study medication must not be mixed with other infusion solutions. Follow the directions given by your doctor closely and use the instructions below as a guide:

1. Wash your hands thoroughly using soap and warm water. The solution must be prepared on a clean and dry surface.
2. Warm the unopened powder vial and the solvent syringe in your hands until they feel as warm as your hands. The material should not be warmer than body temperature (not exceed 37 °C). Wipe any observable moisture from the vial.
3. Remove the cap from the powder vial by gently moving it from side to side several times, whilst at the same time pulling upwards. Remove the stopper attached to the white cap from the syringe (A).
4. Gently screw the syringe on to the powder vial (B).
5. Place the vial on a rigid, non-slip surface and hold it firmly with one hand. Then, strongly press down the fingerplate near the syringe tip using your thumb and index finger (C) until the finger plate meets the top edge of the Bio-Set.
This indicates that the system is activated (D).
6. Connect the plunger rod to the syringe by screwing it into the rubber stopper (E).

7. Inject the solvent by slowly pushing the syringe's plunger down (**F**).
8. Dissolve the powder by gently swirling the vial. Do not shake the vial! Ensure that the powder is completely dissolved before use. Do not use solutions that contain visible particles or that are cloudy (**G**).
9. Invert vial/syringe and transfer the solution into syringe by drawing the plunger out slowly and smoothly (**H**). Ensure that the entire contents of the vial are drawn into the syringe.
10. Apply a tourniquet. Determine the point of injection, clean the skin with an alcohol swab, and prepare site of injection antiseptically as advised by your doctor. Puncture the vein and secure the venipuncture set with a plaster.
11. Unscrew the syringe to disconnect the vial (**I**).
12. Attach the syringe to the venipuncture set by screwing it clockwise and ensure that no blood enters the syringe (**J**).
13. Remove tourniquet!
14. Inject the solution intravenously over several minutes, keeping an eye on the position of the needle. The speed of administration should be based on the subject's comfort, but should not be faster than 2ml/min (maximum rate of *infusion*). (*as of Amd 1*)
15. If a further dose is required, remove the empty syringe by turning it anti-clockwise. Reconstitute the desired amount of product, repeating steps 2. – 9, using a new syringe and connect it to the venipuncture set.
16. If no further dose is required, remove the venipuncture set and syringe. Hold a swab firmly over the injection site on the outstretched arm for approx. 2 minutes. Finally, apply a small pressure dressing to the wound.

NOTE: See accompanying instructions for Injection Set with Filter for injections after blood withdrawal.

[figure not shown]
14.1.2 Presentation of vial and vial adapter (as of Amd 6)

Note: This section was introduced by amendment 6.

How to use BAY 81-818973

- This medicine is intended for injection into a vein only and should be used within 3 hours after reconstitution.
- Use only the items (vial adapter, pre-filled syringe containing solvent and venipuncture set) that are provided with each package of this medicine. If these components cannot be used, please contact your doctor. If any component of the package is opened or damaged, do not use it.
- You must filter the reconstituted product before administration to remove potential particulate matter in the solution. **You are filtering by using the vial adapter.**
- This medicine must **not** be mixed with other infusion solutions. Follow the directions given by your doctor closely and use the **detailed instructions for reconstitution and administration provided in the Annex of this leaflet below.**
- You will need alcohol swabs, gauze pads and plasters.

ANNEX: Detailed instructions for reconstitution and administration for presentation with vial adapter:

[figure not shown]
[figure not shown]
[figure not shown]
[figure not shown]
[figure not shown]
1. Wash your hands thoroughly using soap and warm water.	
2. Warm both an unopened vial and a syringe in your hands to a comfortable temperature (do not exceed 37°C).	
3. Remove the protective cap from the vial (A) and wipe the rubber stopper on the vial with an alcohol swab and allow it to air dry before use.	
4. Place product vial on a firm, non-skid surface. Peel off the paper cover on the vial adapter plastic housing. Do not remove the adapter from the plastic housing. Holding the adapter housing, place over the product vial and firmly press down (B). The adapter will snap over the vial cap. Do not remove the adapter housing at this point.	

Integrated Clinical Study Protocol
 No. BAY 81-8973 / 13400

01 FEB 2019

Version 7.0

Page: 256 of 262

5. Hold the pre-filled water for injections syringe upright, grasp the plunger rod as per the diagram and attach the rod by turning it firmly clockwise into the threaded stopper (C).
	

6. Holding the syringe by the barrel, snap the syringe cap off the tip (D). Do not touch the syringe tip with your hand or any surface. Set the syringe aside for further use.
	

7. Now remove and discard the adapter housing (E).
	

8. Attach the pre-filled syringe to the threaded vial adapter by turning clockwise (F).
	

9. Inject the diluent by slowly pushing down on the plunger rod (G).
	

10. Swirl vial gently until all material is dissolved (H). Do not shake vial. Be sure that the powder is completely dissolved. Inspect visually for particulate matter and discoloration prior to administration. Do not use solutions containing visible particles or that are cloudy.
	

11. Hold the vial on end above the vial adapter and syringe (I). Fill the syringe by drawing the plunger out slowly and smoothly. Ensure that the entire content of the vial is drawn into the syringe. Hold the syringe upright and push the plunger until no air is left in the syringe.
	

12. Apply a tourniquet.
	

13. Determine the point of injection and clean the skin with an alcohol swab.
	

14. Puncture the vein and secure the venipuncture set with a plaster.
	

15. Holding the vial adapter in place, remove the syringe from the vial adapter (the latter should remain attached to the vial). Attach the syringe to the venipuncture set and ensure that no blood enters the syringe (J).
	

16. Remove tourniquet.
	

17. Inject the solution into a vein over 2 to 5 minutes, keeping an eye on the position of the needle. The speed of administration should be based on your comfort, but should not be faster than 2 mL per minute.
	

18. If a further dose needs to be administered, use a new syringe with product reconstituted as described above.
	

19. If no further dose is required, remove the venipuncture set and syringe. Hold a pad firmly over the injection site on your outstretched arm for approximately 2 minutes. Finally, apply a small pressure dressing to the injection site and consider if a plaster is necessary.
	

14.2 Standard of Care

The dosage necessary to achieve hemostasis depends upon the type and severity of the bleeding episode, according to the following general guidelines: (Source: Package Insert Kogenate Bayer). In this protocol, minor surgical procedures are defined as any surgical procedure (elective or emergent) that does not involve general anesthesia and/or respiratory assistance (eg, minor dental extractions, incision and drainage of abscess, or simple excisions). Major surgical procedures are defined as any surgical procedure (elective or emergent) that involves general anesthesia and/or respiratory assistance in which a major body cavity is penetrated and exposed, or a substantial impairment of physical or physiological functions is produced (eg, laparotomy, thoracotomy, craniotomy, fracture).

Degree of hemorrhage/ Type of surgical procedure	Factor VIII level required (%) (IU/dL)	Frequency of doses (hours)/ Duration of therapy (days)
Hemorrhage		
Early hemarthrosis, muscle bleed or oral bleed	20 – 40	Repeat every 12 to 24 hours. At least 1 day, until the bleeding episode as indicated by pain is resolved or healing is achieved.

Degree of hemorrhage/ Type of surgical procedure	Factor VIII level required (%) (IU/dL)	Frequency of doses (hours)/ Duration of therapy (days)
More extensive hemarthrosis, muscle bleed or hematoma	30 – 60	Repeat infusion every 12 – 24 hours for 3 – 4 days or more until pain and disability are resolved.
Life threatening bleeds such as intracranial bleed, throat bleed, severe abdominal bleed	60 – 100	Repeat infusion every 8 to 24 hours until threat is resolved
Surgery		
Minor including tooth extraction	30 – 60	Every 24 hours, at least 1 day, until healing is achieved.
Major	80 – 100 (pre- and postoperative)	a) By bolus injections Repeat infusion every 8 – 24 hours until adequate wound healing occurs, then continue with therapy for at least another 7 days to maintain a factor VIII activity of 30% to 60%

14.3 Healthcare Resources Utilization Questionnaire

The Healthcare Resources Utilization Questionnaire will be used to collect data on the subject. This will include number of days lost from school, medical procedures or laboratory tests, complications, and hospitalizations due to hemophilia or other medical needs. The questionnaire should be administered by the investigator or delegate monthly throughout the study period by interviewing a parent/caregiver. This can be performed either at scheduled study visits, or during regularly scheduled contact between the study site and the parent/caregiver. The answers will be entered on the paper questionnaire by the study site. The completed questionnaire is a source document subject to review by the monitor.

Healthcare Resources Utilization Questionnaire in LEO Kids (13400)

Instructions for the interviewer:

- *Only one parent or caregiver, the person with whom the child relates most closely, should answer the questions consistently*

Integrated Clinical Study Protocol
No. BAY 81-8973 / 13400

01 FEB 2019

Version 7.0

Page: 259 of 262

- Please record the answers in English.
- Please do not write any other information on the form.

Study Center: _____ Subject number: _____

Date of interview: _____ (MM/DD/YYYY)

This form is being completed for the month of _____ and year _____.

For example: Month of June and year 2011 (answers include contacts from June 1 to June 30, 2011).

1. Did your son have any contact with health professionals this past month that were not required as part of the LEO Kids study?

_____ NO _____ YES

If yes, then complete:

Type of contact: _____ Office visit _____ Phone call (Check or enter how many if more than one.)

Reason for contact: _____

Whom did your child see? Please check all that apply:

_____ Hematologist

_____ Family physician

_____ Pediatrician

_____ Nurse

_____ Pharmacist

_____ Other, specify: _____

2. Did your son have any procedures or tests performed in the past month that were not required as part of the LEO Kids study?

_____ NO _____ YES

If yes, please check all that apply:

_____ Blood test Number of times blood was drawn: _____ (even if multiple tubes were collected)

_____ Urine test Number of times specimen collected: _____

_____ Biopsy Number of times: _____

_____ X-ray Number of times: _____ (can include multiple views)

_____ MRI Number of times: _____

_____ CT scan Number of times: _____

_____ Joint surgery Number of times: _____

3. Did your son have any hospital visits in the past month?

_____ NO _____ YES

If yes, check the kind of visit:

_____ Hospital admission. For how many nights? _____ (Include nights in ICU/PICU)

_____ Emergency Department visit. For how many nights? _____

_____ Intensive Care Unit or Pediatric Intensive Care Unit (ICU or PICU).

For how many nights? _____

Reason: _____

4. Did your son miss any days of school due to hemophilia in the past month?

_____ **NO** _____ **YES** If yes, number of days missed? _____ (as of Amd 1)

14.4 Blood draws in subjects weighing less than 10 kg (as of Amd 1)

Every effort has been made to minimize the volumes of blood required for participation in the study. For the majority of subjects in the study, the volumes drawn at any one visit are not expected to exceed more than 1 % of total blood volume, or 3% in any 1 month interval. However, in young infants, Part B of the study may require modification to allow participation by infants or small toddlers. (as of Amd 1)

Table 14.4a shows the estimated total blood volume for children 1-10 kg and the recommended amount of blood for study purposes. These volumes (as of Amd 1) should be considered a guideline, and may be exceeded if determined to be safe by the investigator.

Table 14.4a Recommended Blood Draw Volumes (as of Amd 1)

Body Wt (Kg)	Body Wt (lbs)	Total blood volume (mL)	Allowable volume (mL) in one blood draw (1% of total blood volume)	Total volume (mL) drawn in a 30-day period (3% of total blood volume)
1	2.2	100	1	3
2	4.4	200	2	6
3	6.3	240	2.4	7.2
4	8.8	320	3.2	9.6
5	11	400	4	12
6	13.2	480	4.8	14.4
7	15.4	560	5	16.8
8	17.6	640	6.4	19.2
9	19.8	720	7.2	21.6
10	22	800	8	24

Wt: Body weight/ **Ernst, D. J. Applied Phlebotomy. Lippincott Williams & Wilkins. 2005**

Table 14.4b shows the blood volumes needed for the tubes used for the central laboratory. (as of Amd 1)

Table 14.4b Volume of blood draws in Part B (as of Amd 1)

	Visit 1 Screening	Visit 2 Baseline	Visit 3 ~5 ED	Visit 4 ~10 ED	Visit 5 ~15 ED	Visit 6 20 ED	Interim visit	Final visit 50 ED
Volume of blood (ml)	4.2	5.3	2.7	2.7	2.7	4.1	0	7.7
	7.7							

For infants at least 7 kg at study enrollment, the volumes listed for each individual visit should be well tolerated. As the Screening and Baseline visits can be combined for PUPs, investigators need to be aware that the total volume required could exceed 1% of total blood

volume in children 9 kg or less. The total volume at the combined Screening and Baseline visit may be reduced if the CBC and chemistries are processed through the local laboratory using minimal volumes and the results entered in the CRF. The decision whether to use the local laboratory or to divide the blood sampling over more than one draw is at the investigator's discretion, but the total amount of blood drawn should not exceed 3% of total blood volume over a 30 day interval. (as of Amd 1)

For infants who are 7 kg and smaller at study entry, the sampling schedule will be modified. The sample for collection of HSP-70 antibody (1.2 ml) will not be collected. (as of Amd 1) FVIII trough level and inhibitor will be measured using a reduced volume (1.8 ml). Estimated blood volumes based upon these modifications are shown in table 14.4c. (as of Amd 1)

Table 14.4c Modified volume of blood in infants less than 7 kg (as of Amd 1)

	Visit 1 Screening	Visit 2 Baseline	Visit 3 ~5 ED	Visit 4 ~10 ED	Visit 5 ~15 ED	Visit 6 20 ED	Interim visit	Final visit 50 ED
Volume of blood (ml)	2.4	4.1	2.7	2.7	2.7	4.1	0	6.5
	6.5 (5.2) ^a							

a. (...) Est volume if CBC and chemistries obtained with minimal volumes through local laboratory

For infants less than 7 kg, for whom the Screening and Baseline visits are combined, it is recommended that the screening CBC and chemistries be processed through the local laboratory using minimal volumes, and the results entered in the CRF. Capillary samples may be used if care is used to minimize the risk of hemolysis. It is assumed that the minimal volume needed for both CBC and chemistries is approximately 1.1 ml. (as of Amd 1)

Should an investigator wish to enroll a subject who weighs less than 5 kg, discussion with the sponsor is required. (as of Amd 1)

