5.1.2 Exclusion criteria

Subjects who meet any of the following criteria at Screening or Baseline visits will be excluded from participating in the study:

Parts A and B

1. Any individual with another bleeding *disorder (as of Amd 1)* that is different from Hemophilia A (eg, von Willebrand disease, Hemophilia B)
2. Any individual with thrombocytopenia (platelet count $< 100\ 000/\text{mm}^3$)
3. *Creatinine $> 2x$ upper limit of normal or Aspartate aminotransferase (AST)/Alanine aminotransferase (ALT) $> 5x$ upper limit of normal (as of Amd 1)*
4. Any individual without *a* negative inhibitor testing *at screening* (except for PUPs) (as of Amd 3)
5. Any individual who is receiving *chemotherapy, immune modulatory drugs (Intravenous immunoglobulin [IVIG], cyclosporine, chronic use of oral or i.v. corticosteroids), has received another investigational FVIII product* within the last month, or received another experimental drug within *the last 3 months. (as of Amd 1, Amd 3)*
6. Any individual who requires any pre-medication to tolerate FVIII *treatment (as of Amd 1)* (eg, antihistamines)

7. Any individual who is unwilling to comply with study visits or other protocol requirements, for example (eg. prophylaxis treatment) or is not suitable for participation in this study for any reason, according to the Investigator's **judgment. (as of Amd 1)**
8. Known hypersensitivity to active substance, mouse, or hamster protein.
9. Previous participation in this study

Part B only (*PUPs/MTPs [as of Amd 6]*):

10. First treatment with BAY 81-8973 **for high risk bleeding situations (eg, surgery, intracranial bleed), or requiring intensive or prolonged treatment. (as of Amd 1)**
11. **Unable to tolerate volume of blood draws required for study participation (See Section 14.4). (as of Amd 1)**

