7.1.2.1 Visit 1 – Screening

At the screening visit, the following procedures and assessments will be performed:

- Obtain written informed consent from the parents/legal representative. *Assent should be (as of Amd 1) obtained from subjects, depending on their age and intellectual status or according to local practice. (as of Amd 1)*
Note: No Screening procedures may be performed unless written informed consent (and assent, if applicable) has been obtained. (see Section 11.2)
- *Assignment (as of Amd 1) of a unique PID number (see Section 5.3)*
- Eligibility check
No subject may *receive treatment with study drug (as of Amd 1)* unless all *inclusion and exclusion criteria are met (as of Amd 1)* as given in Section 5.1. Confirmation of selection criteria may be based on medical records, but laboratory test results must confirm eligibility. The severity of *hemophilia may be based on documented FVIII level at diagnosis. (as of Amd 1)*
- Recording of *demographic data, medical and surgical history, and any adverse events (AEs) occurring after signing of informed consent. (as of Amd 3)*
- Recording of prior and concomitant medication *and Healthcare Resources Utilization Questionnaire. (Appendix 14.3). (as of Amd 1)*

- Measurement of vital signs: Systolic and diastolic blood pressure, heart rate, and body temperature. **Blood pressure may be deferred if appropriate cuff size or equipment is not available. (as of Amd 1)**
- Physical examination including measurement of body height/*length* and weight
- Blood samples for laboratory tests:
 - Complete blood count (CBC)
 - **Serum chemistry (sodium [Na], potassium [K], bicarbonate [CO], chloride [Cl], creatinine, alanine and aspartate aminotransferases [ALT, AST], total bilirubin. (See Section 14.4 for children <10 kg) (as of Amd 1)**
- **FVIII:C level for PUPs and MTPs, inhibitor testing (not required for PUPs but required for MTPs incl. a retention sample for ELISA) (as of Amds 1 and 6)**
- **Training on and dispensing (as of Amd 1) of the EPD. Note: the EPD may be given to the subjects to take home at any time between Screening and Baseline, but no entries are to be made before the first injection at Baseline (as of Amd 3).**

In case of MTPs, the screening visit should only take place after a washout period of at least 48 h following any previous treatment with any FVIII replacement product (as of Amd 6).

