8.4 Statistical and analytical plans

The data will be summarized using the software package SAS release 9.1 or higher (SAS Institute Inc., Cary, North Carolina [NC], United States of America [USA]). All data will be listed and summary tables will be provided. The number of data available and missing data, mean, standard deviation, and other summary statistics will be calculated for continuous data. Frequency tables will be generated for categorical data. No formal statistical tests will be performed.

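### Protocol Section 14.4 contradicts itself on blood volumes for infants of 7 kg or less, and its Screening and Baseline figures were not updated for minimally treated patients (MTPs)

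*Protocol*

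**What the plan says.** Section 14.4 gives the standard Part B volumes in Table 14.4b ("Volume of blood (ml) 4.2 5.3 2.7 2.7 2.7 4.1 0 7.7", running from Screening to Final, with 7.7 ml for a combined Screening and Baseline visit). For infants of 7 kg or less the text then makes two changes. First, "The sample for collection of HSP-70 antibody (1.2 ml) will not be collected". Second, "FVIII trough level and inhibitor will be measured using a reduced volume (1.8 ml". It goes on: "Estimated blood volumes based upon these modifications are shown in table 14.4c".

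Table 14.4c reads Screening 2.4, Baseline 4.1, Visits 3, 4 and 5 2.7 each, Visit 6 4.1, Interim 0 and Final 6.5 ml. The combined visit is 6.5 ml, or 5.2 ml if CBC and chemistry go to the local laboratory. On the local-laboratory option the text says: "It is assumed that the minimal volume needed for both CBC and chemistries is approximately 1.1 ml".

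Table 14.4c carries the Amendment 1 label. MTPs became eligible with Amendment 6. Section 7.1.2.1 now lists, at Screening, an FVIII:C level and "inhibitor testing (not required for PUPs but required for MTPs incl. a retention sample for ELISA". Footnote h of Table 7-2b requires central inhibitor testing of MTPs at Screening, and both central and local testing at Baseline.

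Part B exclusion criterion 11 points to these volumes: "Unable to tolerate volume of blood draws required for study participation (See Section 14.4".

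**The concern.** The text says both changes are built into Table 14.4c, yet the visits that draw nothing except the trough and inhibitor sample show no change. The Screening figure is also no larger than CBC and chemistry alone, although MTPs must now give more blood than that at Screening.

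An investigator who applies criterion 11 to a small infant is sent to Section 14.4. There the text and the table give different sample volumes, and for an MTP the Screening volume is too small. At stake is a tolerance judgement in the smallest children, made on volumes that conflict or are out of date.

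**Working it through.** **Inputs.** Tables 14.4a, 14.4b and 14.4c, the 1.2 ml HSP-70 sample, the 1.8 ml reduced sample and the 1.1 ml local CBC/chemistry volume, all from Section 14.4. Visit content comes from Table 7-2b and Sections 7.1.2.1 to 7.1.2.8.

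**Step 1: components.**
- Trough plus inhibitor: 2.7 ml. It is the only routine sample at Visits 3-5; PK sampling is optional and closed to infants under 9 kg, and the biomarker sample is a one-off with separate consent.
- Recovery: Visit 6 minus Visit 5 = 4.1 - 2.7 = 1.4 ml.
- HSP-70: 1.2 ml.
- CBC plus chemistry: 6.5 - 5.2 + 1.1 = 2.4 ml. Table 14.4b agrees: 7.7 - 5.3 = 2.4.
- Remainder at Screening in Table 14.4b: 4.2 - 2.4 = 1.8 ml for FVIII/inhibitor.

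**Step 2: rebuild Table 14.4b.** Baseline 2.7 + 1.4 + 1.2 = 5.3. Visit 6 2.7 + 1.4 = 4.1. Final and combined visit 2.4 + 2.7 + 1.4 + 1.2 = 7.7. Every cell is reproduced.

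**Step 3: apply the declared changes** (ml). The second change is 2.7 - 1.8 = 0.9 ml wherever the trough and inhibitor sample is drawn.

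| Visit | 14.4b | 14.4c printed | HSP-70 removed only | Both changes | Printed minus both |
|---|---|---|---|---|---|
| Screening | 4.2 | 2.4 | 4.2 | 4.2 | -1.8 |
| Baseline | 5.3 | 4.1 | 4.1 | 3.2 | +0.9 |
| Visits 3, 4, 5 (each) | 2.7 | 2.7 | 2.7 | 1.8 | +0.9 |
| Visit 6 | 4.1 | 4.1 | 4.1 | 3.2 | +0.9 |
| Final | 7.7 | 6.5 | 6.5 | 5.6 | +0.9 |
| Combined | 7.7 | 6.5 | 6.5 | 5.6 | +0.9 |
| Combined, local laboratory | not given | 5.2 | 5.2 | 4.3 | +0.9 |

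From Baseline on, and for the combined visit, the printed table matches HSP-70 removal alone. The only cell that moves by 1.8 ml is Screening (4.2 to 2.4). That is the full FVIII/inhibitor remainder from Step 1, so the sample has been removed there, not reduced.

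**Step 4: Screening for MTPs.** Printed 2.4 ml = CBC plus chemistry, which leaves 0 ml for anything else. The documents do not give the MTP Screening sample volume. Assuming 1.8 ml (the remainder in Table 14.4b) to 2.7 ml (the later-visit sample), the total is 2.4 + 1.8 = 4.2 to 2.4 + 2.7 = 5.1 ml, plus an ELISA retention volume that is not stated.

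**Step 5: Baseline for MTPs.** The added local inhibitor test has no volume in the table. The 3.2 ml figure, and the 0.9 ml difference at Baseline, therefore hold for PUPs only. The combined visit is open to PUPs only.

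**Step 6: against the 1% guideline.** Table 14.4a gives 400 ml total blood volume at 5 kg, that is 80 ml/kg, so 1% is 0.8 ml/kg, or 4.0 ml at 5 kg.
- Baseline and Visit 6: printed 4.1 ml exceeds 4.0 ml; 3.2 ml does not (at Baseline, PUPs only). The printed value crosses 1% below 4.1 / 0.8 = about 5.1 kg.
- MTP Screening: printed 2.4 ml is within 4.0 ml; 4.2 ml or more is not. The crossing is below 4.2 / 0.8 = 5.25 kg, or 5.1 / 0.8 = about 6.4 kg at the upper assumption.
- Combined visit with local laboratory: 5.2 / 0.8 = 6.5 kg against 4.3 / 0.8 = about 5.4 kg.
- Visits 3-5: 2.7 / 0.8 = about 3.4 kg, so neither value matters at 5 kg or more.
- Final: 5.6 / 0.8 = 7.0 kg, so below 7 kg both 6.5 and 5.6 ml exceed 1%.

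**The case against.** The strongest reply is that the documents prove a contradiction, not which side is wrong. One rule reproduces every cell of Table 14.4c: remove the HSP-70 sample and remove the 1.8 ml Screening sample. On that reading the table is coherent and the 1.8 ml sentence is misworded. The tubes used are left to the laboratory manual, which is not among the documents. This stands. A reader might infer that Table 14.4c is simply too high, by 50% at Visits 3-5 (2.7 / 1.8) or by 31% from Baseline to Final (22.8 / 17.4 ml). Both figures presuppose that the sentence is the true one. The 17.4 ml total also leaves out the MTP local test, and Section 14.4 sets no limit on a Baseline-to-Final sum.

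A reader might also infer that eligible infants are being kept out. The documents do not show this. Criterion 11 asks whether the child can tolerate the draws and sets no numeric cut-off. The volumes are a guideline that the investigator may exceed if judged safe, sampling at the combined visit may be divided, and enrolment below 5 kg already requires discussion with the sponsor.

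For PUPs, the missing Screening FVIII volume is not a firm omission, because Section 5.1.1 lets severity rest on documented prior testing.

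None of this reconciles the sentence with Visits 3-6, or supplies the missing MTP samples. Nor is it a fault of text extraction: the same figures appear in the Amendment 1 copy of the tables in Section 13.1.2.2, and the component sums close.

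**Conclusion.** The point holds in two parts of different strength.

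The text and Table 14.4c cannot both stand. The conflict is 0.9 ml per trough and inhibitor sample at Visits 3-6 and Final, and for PUPs also at Baseline and the combined visit. Which side is in error is open.

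The MTP Screening figure of 2.4 ml is too low whichever side is right, because it has no room for the samples now required. The size of the shortfall, at least 1.8 ml, rests on the assumed 1.8-2.7 ml sample and excludes the ELISA volume. MTP Baseline likewise lacks the local inhibitor test.

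The practical effect is confined to tolerance judgements in the smallest infants, chiefly near 5 kg, where the apparent position against 4.0 ml reverses for Baseline, Visit 6 and MTP Screening. The stronger claim that the table is wrong in both directions goes further than the documents allow, because the overstatement is conditional. No efficacy result or inhibitor estimate changes.

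**What to change.** Check the laboratory manual, then correct whichever of the 1.8 ml sentence and Table 14.4c is wrong. Add MTP entries for Screening (CBC, chemistry, FVIII, inhibitor, ELISA retention) and for Baseline (central plus local inhibitor test), with their volumes stated. In the same edit, reconcile the weight boundary: the text includes infants of exactly 7 kg, while the title of Table 14.4c covers only those below 7 kg. The cost is one table and one or two sentences in the next amendment, with no additional samples.
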